3.2 Treatment Algorithm for Multiple DEB-TACE procedures

Patients who meet the eligibility criteria in Section 4.0 with a lesion or lesions supplied by more than one segmental hepatic artery branch will be considered for up to four sequential DEB-TACE procedures intended to target the entire tumor vascular supply in a step-wise fashion. The number of procedures will be based on the number, location, and size of the lesions as well as on the hepatic arterial anatomy up to a maximum of 4 DEB-TACE procedures. This information will be obtained from the pre-procedure cross-sectional imaging (CT or MRI), hepatic artery angiography, and C-arm CT (when applicable).

Sequential DEB-TACE may be offered in the following settings:

- A. Multifocal HCC (UNOS T2 or T3 disease; no radiographic evidence of macrovascular invasion or extracapsular extension)
- B. Single HCC greater than 3 cm (UNOS T2 or T3 disease without radiographic evidence of macrovascular invasion or extracapsular extension).
- C. More than 1 segmental feeding hepatic artery branch to a lesion of any size.

Pre-procedure evaluation will be the same as for patients undergoing one DEB-TACE procedure (Table 2). For each DEB-TACE procedure, up to two 2 ml vials of 100-300 μ m LC-Beads[®] impregnated per manufacturer-supplied protocol with 25mg of doxorubicin per ml of beads will be administered into the catheterized hepatic artery. Procedure will be stopped when arterial flow approaches stasis and/or when the entire DEB dose has been administered.

Sequential DEB-TACE procedures will be performed approximately 1 month apart. Longer intervals between the procedures may be necessary. The timing of DEB-TACE will be determined by the treating interventional radiologist and hepatologist or medical oncologist. The number of procedures (up to 4 total) will be based on the number, location, and size of the lesions as well as on the hepatic arterial supply to the lesions. This information will be obtained from the pre-procedure cross-sectional imaging (CT or MRI) and hepatic artery angiography. This step-wise approach is intended to target the entire tumor vascular supply in a step-wise fashion prior to assessing response to therapy.

The maximum administered doxorubicin dose per DEB-TACE procedure (session) will be 100mg (50 mg per each 2 ml vial of 100-300 μ m LC beads). The maximum administered dose as a result of four DEB-TACE procedures will be 400 mg.

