6.0 TREATMENT PLAN

Segmental hepatic artery catheterization will be performed via femoral artery approach using a combination of 3-French, 4-French, and 5-French angiographic catheters. Segmental DEB-TACE will be performed using two 2ml vials of LC beads (Biocompatibles, Inc.) impregnated per standard manufacturer-supplied protocol with a total of 100 mg of doxorubicin (25 mg per milliliter of beads). Microspheres in the size range of 100-300 μ m will be used. Procedure will be stopped when arterial flow approaches stasis and/or when the entire DEB dose has been administered.

Patients with multiple liver lesions, lesions >3 cm, or lesions with more than 1 feeding branch hepatic artery may receive additional DEB-TACE at approximately 1 month intervals. Cross-sectional imaging (contrast-enhanced CT or MRI) will be performed approximately 1 month after targeting of all hepatic lesions in the course of 1-4 DEB-TACE procedures. Patients with residual or recurrent disease may receive up to 4 total DEB-TACE procedures.

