Approximately one month after last planned DEB-TACE procedure, patients will undergo repeat cross-sectional imaging with multi-phase contrast-enhanced CT or MRI of the abdomen. First follow-up imaging study will be obtained no more than 6 months following the first DEB-TACE procedure. Subsequent imaging will be performed at approximately 3 month-intervals until 360 days following DEB-TACE. Standard clinical practices will be adhered to during the follow-up period.

Response to treatment will be assessed according to RECIST version 1.1 and mRECIST criteria (see section 9.2).

Patients will be removed from study and follow-up assessments will stop prior to 360 days following DEB-TACE if a patient:

- a) requires > 4 DEB-TACE procedures
- b) requires another anti-cancer treatment modality such as ablation, surgery, or conventional TACE

- c) receives a liver transplant
- d) develops untreatable intrahepatic or extrahepatic disease progression
- e) experiences unacceptable toxicity (see section 10.1). All serious adverse events will be followed until the SAE has been resolved.

Pathology report describing the extent of HCC in the liver explant will be reviewed for the subset of patients who undergo LT.

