12.3 Analysis Plan

Demographics and Baseline Characteristics

Demographic and baseline laboratory results will be summarized using descriptive statistics.

Safety Analysis

Patients will be monitored for development of recognized complications of DEB-TACE including liver dysfunction, renal dysfunction, ascites, hepatic encephalopathy, hepatorenal syndrome, biliary injury (stricture or leak), cholangitis, cholecystitis, hepatic abscess, abdominal pain, nausea, vomiting, fatigue, and fever. Adverse events will be graded according to NCI CTCAE version 4.03. Prevalence of adverse events will be summarized using descriptive statistics.

Efficacy Analyses

Analyses will be performed using the intent to treat population with exceptions as defined below, which require patient replacement.

Primary efficacy analysis

Primary efficacy will be evaluated as 1-month radiographic response after last DEB-TACE procedure in treated HCC lesions according to 1) RECIST version 1.1 and 2) mRECIST. Patients who do not have any post-baseline tumor assessments will be counted as non-responders. Point estimates of response rate and confidence intervals will be provided.

Secondary efficacy analyses

1. Overall radiographic response by 1) RECIST 1.1 and 2) mRECIST 6 months after the date of the first planned DEB-TACE procedure. This analysis will take into account all measurable hepatic HCC lesions present on cross-sectional imaging 6 months after the date of the first planned DEB-TACE procedure.
2. Time to untreatable progression (TTUP). TTUP is defined as time to disease progression untreatable by liver-directed percutaneous or surgical methods as assessed by treating investigator(s). Patient follow-up up to 1 year after last DEB-TACE will be allowed for this outcome variable.
3. Time to progression (TTP). TTP is defined as the time interval between date of first DEB-TACE procedure and date of imaging documenting development of intra- or extrahepatic disease progression by 1) RECIST 1.1 and 2) mRECIST. Patient follow-up up to 1 year after last DEB-TACE will be allowed for this outcome variable.

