4. Hepatic progression-free survival (HPFS). Hepatic progression-free survival rate will be defined as the number of patients who neither progressed in the treated regions of the liver (using RECIST 1.1 and mRECIST) nor died before 1, 3, 6, 9, and 12 months after date of last DEB-TACE over the number of patients who entered the trial at these same timepoints. Estimates of the HPFS curves from the Kaplan-Meier method will be presented. Median progression event time and a 2-sided 95% confidence interval for the median will be provided using a normal approximation. For each stratum, the median, 25th and 75th percentile for HPFS will be provided.
5. Progression-free survival (PFS). Progression-free survival rate will be defined as the number of patients who neither progressed (using RECIST 1.1 and mRECIST) nor died before 1, 3, 6, 9, and 12 months after date of last DEB-TACE over the number of patients who entered the trial at these same timepoints. Estimates of the PFS curves from the Kaplan-Meier method will be presented. Median progression event time and a 2-sided 95% confidence interval for the median will be provided using a normal approximation. For each stratum, the median, 25th and 75th percentile for PFS will be provided.
6. Overall Survival (OS) is a secondary efficacy endpoint and will be analyzed 12 months after the last patient is enrolled. OS will be calculated from date of first DEB-TACE until date of death, using chart review and/or follow up phone calls to determine date of death in patients after removal from study. The survival of patients who are permanently lost to follow-up or still alive after 360 days of follow up post study discontinuation will be censored on the date the patient is last-contacted or last known to be alive. Estimates of the OS curves from the Kaplan-Meier method will be presented.
7. Proportion of patients who remain active on the waitlist and are eventually transplanted is a secondary clinical endpoint. This data will be presented using Kaplan-Meier method
8. Proportion of patients who are inactivated or drop out from the wait list for any reason but transplantation will be determined. Reasons for inactivation and/or removal from waitlist will be tabulated.
9. Proportions of patients who are successfully down-staged and achieve active waitlist status and eventually are transplanted will be determined.

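### PFS and HPFS rates are counted from the last DEB-TACE while TTP and OS are counted from the first, so the clock for multi-session patients starts late and the Kaplan-Meier origin is left open

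*Combined protocol and SAP*

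**What the plan says.** Section 12.3, secondary efficacy items 4 and 5, defines the HPFS and PFS rates through patients who neither progressed nor died "before 1, 3, 6, 9, and 12 months after date of last DEB-TACE". The same items promise Kaplan-Meier curves and medians but do not say from which date those curves start.

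The neighbouring items use another origin. For item 3, "TTP is defined as the time interval between date of first DEB-TACE procedure and date of imaging documenting development" of progression. For item 6, "OS will be calculated from date of first DEB-TACE until date of death".

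The two origins separate when there is more than one session. Section 3.2 allows "up to a maximum of 4 DEB-TACE procedures" and states that "Sequential DEB-TACE procedures will be performed approximately 1 month apart"; section 8.3 permits intervals up to 90 days. In Table 3 (multiple procedures) the abdominal and chest imaging rows are marked only at screening. Section 8.4.2 places the first follow-up scan after the course: "Approximately one month after last planned DEB-TACE procedure, patients will undergo repeat cross-sectional imaging", and no later than six months after the first procedure. Section 6.0 adds that "Patients with residual or recurrent disease may receive up to 4 total DEB-TACE procedures".

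The Abstract expects most patients to need a single session.

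**The concern.** A time-to-event origin should be a date fixed at or near entry. The last DEB-TACE is a later date, and under section 3.2 it depends on lesion number, size, location and arterial supply. Three things follow for patients with more than one session.

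- If last means last received, nobody can die between the first session and the PFS origin, so that interval is death-free by construction.
- Progression that arises at any time during the course is first seen on the scan about one month after the last planned session. On the PFS clock it falls in month 1, whatever the length of the course.
- If progression is documented before the last session, it has a negative time on the PFS clock. This could come from the imaging between sessions that a Table 3 footnote mentions, or from an early scan followed by retreatment under section 6.0.

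At stake is whether the landmark rates and curves mean the same thing for every patient, and whether they can be read beside TTP and OS.

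**Working it through.** The plan gives no PFS or HPFS figure to reproduce. Its two-stage design figures concern response; they reproduce (early stopping 75.8% at a 20% response rate and 12.6% at 40%; alpha 4.87%; power 85.4%) and do not depend on this point.

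**Shift of the clock.** Inputs: one to four sessions and about 30 days between them (section 3.2); first scan about 30 days after the last planned session and within six months of the first (section 8.4.2).

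- Gap from first to last session = (sessions − 1) × interval.
- First scheduled scan, which is also the 1-month PFS landmark = gap + 30 days.
- 12-month landmark = gap + 360 days.
- Largest gap that meets the six-month scan limit = 180 − 30 = 150 days.

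**Illustration of size.** Assumption, not in the documents: one constant hazard from the first DEB-TACE for all patients, with a median of 9 months (range 6 to 12). Event-free share at the 1-month landmark = 0.5^((1 + gap in months)/median).

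| Sessions | Gap (days) | 1-month landmark, days from first session | 12-month landmark, days from first session | Event-free at 1-month landmark, median 6 / 9 / 12 months |
|---|---|---|---|---|
| 1 | 0 | 30 | 360 | 89.1 / 92.6 / 94.4% |
| 2 | 30 | 60 | 390 | 79.4 / 85.7 / 89.1% |
| 3 | 60 | 90 | 420 | 70.7 / 79.4 / 84.1% |
| 4 | 90 | 120 | 450 | 63.0 / 73.5 / 79.4% |
| Scan-limit case | 150 | 180 | 510 | 50.0 / 63.0 / 70.7% |

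A progression found on the first scheduled scan of a four-session patient is therefore recorded at 30 days for PFS and 120 days for TTP.

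Three or four sessions at 90-day intervals would put the first scan on day 210 or 300, past the six-month limit. Sections 8.3 and 8.4.2 need reconciling on this. Here the scan limit serves only to bound the gap.

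**Pooled effect.** The documents do not give the session mix. Assume 70% with one session and 10% each with two, three and four, at 30-day spacing:

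- Median 9: 0.7 × 92.6 + 0.1 × (85.7 + 79.4 + 73.5) = 88.7%, against 92.6% on a first-session clock, a shift of 3.9 points.
- Median 6: 0.7 × 89.1 + 0.1 × (79.4 + 70.7 + 63.0) = 83.7%, a shift of 5.4 points.
- Median 12: 0.7 × 94.4 + 0.1 × (89.1 + 84.1 + 79.4) = 91.3%, a shift of 3.1 points.
- Median 9 with 80% or 60% single-session and the rest split equally: 90.0% or 87.4%, shifts of 2.6 or 5.2 points.

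Standard error at 51 patients: √(0.887 × 0.113 / 51) = 4.4 points. The pooled shift is about one standard error.

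**Progression before the last session.** Take one session on day 0, treatable progression on the day-30 scan, and retreatment on day 60, inside the 90-day allowance. Section 10.3 removes patients for untreatable intrahepatic or for extrahepatic progression, so this patient stays on study. TTP is 30 days. On the PFS clock the event falls at 30 − 60 = −30 days. Read literally, the rate in item 5 counts this patient as failed at 1, 3, 6, 9 and 12 months, because the progression precedes all of those dates. A Kaplan-Meier curve starting on day 60 cannot place the event, and the plan does not say what to do.

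**The case against.** The last-session origin has a rationale: the landmarks at 1, 3, 6, 9 and 12 months match the scans scheduled 30, 90, 180, 270 and 360 days after the last planned session. Moving the origin breaks that match for multi-session patients. Most patients should have one session, and TTP and OS already start at the first. The endpoints are secondary, in a single-arm trial with no test on them. Imaging between sessions is also contemplated, through the Table 3 footnote and the section 4.2 requirement to meet entry criteria before each session. All of this stands and limits the size of the point. It does not supply a Kaplan-Meier origin or align PFS with TTP and OS, and imaging between sessions makes a progression before the origin more likely.

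Three stronger readings are tempting, and the documents do not support them.

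- A reader might infer that the absence of scans between sessions by itself puts progression before time zero. Progression is dated by imaging, so an event found on the scheduled scans is dated after the last session. Only undetected progression, or progression on an unscheduled or early scan followed by retreatment, precedes the origin.
- A reader might infer that a patient who recurs at six months and is then retreated would be reported as progression-free. Retreatment after so long a gap exceeds the 90-day interval in section 8.3, and the literal rate would count that patient as failed. The event disappears only if the clock is restarted, and the plan contains no such rule.
- A reader might infer that the PFS rates cannot be interpreted at all. With most patients on identical origins and a pooled shift near one standard error, that goes too far. Nor is a common hazard likely to hold exactly, since multiple sessions go to more extensive or more complex disease.

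**Conclusion.** The inconsistency is real and confined. The HPFS and PFS rates use a post-enrolment origin that varies with the number of sessions, TTP and OS do not, and the curves have no stated origin. The clock shift is 30 to 90 days for two to four sessions at 30-day spacing and at most about 150 days under the six-month scan limit; these figures follow from the documents. The effect lies in multi-session and retreated patients. Its size in percentage points rests on the assumed hazard and session mix: about 3 to 5 points in the pooled 1-month rate. The claim that the pre-origin interval is death-free holds if last means last received, which the plan does not state. Sample size, stopping rules and the primary response analysis are unaffected. The change should be made because it is cheap and removes an avoidable ambiguity.

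**What to change.** In section 12.3, items 4 and 5, define PFS and HPFS from the date of the first DEB-TACE for both the rates and the Kaplan-Meier curves, as for TTP and OS. State that the first documented progression is the event even if further DEB-TACE follows.

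The cost is wording only: no new scans, data or patients. The drawback is that landmarks no longer line up with scan days for multi-session patients, who may have no scan until about day 60 to 120 at 30-day spacing. Flag the 1- and 3-month rates as uninformative for them. The last-session landmarks may be kept as a supplementary display. An interval-censored sensitivity estimate, from last negative to first positive scan, is optional.

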10.3 CRITERIA FOR PATIENT REMOVAL FROM STUDY

Patients will be removed from study for any of the following events:

- Unacceptable toxicity (listed above in section 10.1),
- Other toxicity which investigator deems to place the patient at significant risk for toxicity
- Withdrawal of consent
- Noncompliance or inability to meet requirements of protocol
- Requirement for >4 DEB-TACE procedures
- Requirement for another anti-cancer treatment modality such as ablation, surgery, conventional TACE
- Receives a liver transplant
- Develops untreatable intrahepatic tumor progression
- Develops extrahepatic tumor progression

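### Survival tracing ends 360 days after study discontinuation, which depends on prognosis, so Kaplan-Meier OS beyond about 12 months can be biased in either direction

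*Combined protocol and SAP*

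**What the plan says.** Section 12.3, secondary efficacy item 6, sets five things for OS.

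- Clock: "OS will be calculated from date of first DEB-TACE until date of death".
- Deaths after removal are still sought, "using chart review and/or follow up phone calls to determine date of death in patients after removal from study".
- Censoring: patients permanently lost, or "still alive after 360 days of follow up post study discontinuation will be censored on the date the patient is last-contacted" or, as the sentence goes on, last known alive.
- Timing: OS "will be analyzed 12 months after the last patient is enrolled".
- Estimator: "Estimates of the OS curves from the Kaplan-Meier method will be presented". No landmark time, common follow-up limit or sensitivity analysis is given.

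Section 10.3 lists the removal criteria. They include "Develops untreatable intrahepatic tumor progression", "Develops extrahepatic tumor progression", "Receives a liver transplant", unacceptable toxicity, and the need for another anti-cancer modality. Sections 8.4.1 and 8.4.2 repeat most of this list and stop study assessments at that point. Patients who are not removed are followed for one year (Section 3.0). The plan does not say whether finishing that year counts as study discontinuation.

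**The concern.** Kaplan-Meier assumes that patients censored at a given time have the same later hazard as those still at risk. Here the time at which tracing may stop is the removal date plus 360 days, and removal is itself an outcome. A patient removed in month 3 who survives the next 360 days can leave the risk set at about month 15. A single-procedure patient who completes the year stays until about month 24, or until the data cut-off if completion is not discontinuation. If the two groups differ in hazard, the curve after month 12 is weighted toward the group that stays.

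This is separate from ordinary administrative censoring. The study may run for five years, so early enrollees could have long survival records, yet the rule does not require those records to be collected or used. The period affected matters in this population: Section 1.1 gives a typical transplant wait of 1.5-2 years. Section 2.0 also plans to test AFP response for association with OS.

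**Working it through.** **Plan's own figures.** The plan states no figure for OS. Its only reproducible figures belong to the response design, and they hold: with 4 or fewer of 17 as the stopping bound, P(stop) = 0.758 at a 20% response rate and 0.126 at 40% (stated 76% and 13%). With 15 or more of 51 needed, type I error is 0.0487 and power 0.854. Nothing below bears on them.

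**When the rule can first act.** Earliest censoring = earliest removal + 360 days. Removal cannot precede time zero (first DEB-TACE) for a patient on the OS clock, so the rule censors nobody before day 360.

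**One worked case (assumed inputs).** Half the patients are removed for progression, spread evenly over months 0-6. Median survival after removal is 9 months, a hazard of ln 2/9 = 0.0770 per month. Everyone else has hazard 0.01 per month. There are no transplants.

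- True survival of progressors at 23.5 months, averaged over removal time: exp(-0.0770 × 23.5) × [exp(0.0670 × 6) - 1]/(0.0670 × 6) = 0.164 × 1.231 = 0.201.
- True OS: 0.5 × exp(-0.235) + 0.5 × 0.201 = 0.395 + 0.101 = 0.496.
- Kaplan-Meier is correct at month 12: 0.5 × exp(-0.12) + 0.5 × 0.488 = 0.688.
- Between months 12 and 18 the surviving progressors are censored one by one. Integrating the hazard among those still at risk gives a conditional survival of 0.872, so the curve reads 0.600 at month 18.
- After month 18 only stable patients remain: 0.600 × exp(-0.01 × 5.5) = 0.568.
- Error at 23.5 months: 57% against 50%, about +7 points.

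**Other assumed cases** (simulation; Kaplan-Meier minus truth, in points; completers censored a year after completion):

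| Removal pattern | 12 mo | 18 mo | About 24 mo |
|---|---|---|---|
| Equal hazards in all groups | 0.0 | 0.0 | 0.0 |
| Progression only, 2-10% per month, hazard ratio 2-10 | 0.0 | up to +1.4 | up to +3.3 |
| Transplant only, 3% per month | 0.0 | -0.5 | -1.4 |
| Mixed progression and transplant, three cases | 0.0 | -0.3 to +0.2 | -1.1 to +0.3 |

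The transplant and mixed rows use Section 1.1's survival ranges: 80% at five years after transplant (range 70-90%) and 35% with liver-directed therapy alone (range 20-50%). These convert to monthly hazards of -ln(0.80)/60 = 0.0037 and -ln(0.35)/60 = 0.0175. A separate transplant-only simulation reached about -2 at 24 months. Removal rates and hazard ratios are assumptions throughout.

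**If completers are not discontinued** and are followed to the cut-off, the curve extends further. The error at 36 months then runs from +5.1 (progression only, hazard ratio 6) to -3.7 (transplant only).

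**Sampling error.** With 51 patients the SD of the Kaplan-Meier estimate is about 6-7 points at 18 months and 7-8 at 24 months.

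**After the fix.** With everyone followed to one common cut-off, the error was 0.0 points at 12, 18, 24, 30 and 36 months in every case tested.

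**The case against.** Several points on the other side are sound.

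- A reader might infer that early failures are censored first. The text does not support this. Deaths after removal are actively sought and count as events; only those who survive the 360-day window are censored.
- A reader might infer that OS is overstated. Transplant also triggers removal and carries a good prognosis, so it pulls the curve down. Needing ablation, surgery or conventional TACE need not mean a poor prognosis either. The direction cannot be fixed from the documents.
- A reader might infer a hard stop at removal plus 360 days that discards later data. The text does not say so. The last-known-alive wording could admit later dates. That does not rescue the estimate, because the length of follow-up would then depend on who happens to stay in contact.
- The largest figure rests on strong assumptions. Removal requires untreatable or extrahepatic progression, not any progression. A 1% monthly hazard implies exp(-0.60) = 55% five-year survival, above Section 1.1's 20-50% for liver-directed therapy alone, which widens the contrast.
- OS is secondary. Item 6 promises curves only; medians and percentiles are specified for hepatic PFS and PFS. OS plays no part in the sample size or stopping rules.

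These points limit the size and the wording. They do not remove the link between removal and the end of tracing. Nor does the sampling error dispose of it, since a confidence interval does not show this kind of bias.

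**Conclusion.** The point stands in a limited form. Survival tracing is tied to a discontinuation date that depends on prognosis, and the plan does not address it, so Kaplan-Meier OS after about 12 months can be biased. Under the assumed removal rates and hazards, the error at about 24 months is roughly -2 to +7 points, near zero when progression and transplant removals offset, and mostly below the sampling error with 51 patients. There is none if hazards do not differ by removal status. The rule causes none up to 12 months. The documents do not support saying that OS is biased, or biased upward. The consequence is confined to the later part of a secondary curve and to analyses that use it. This is a cheap improvement, not a flaw in the primary analysis.

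**What to change.** In Section 12.3 item 6, delete the limit of 360 days after discontinuation. For every treated patient, whatever the date of or reason for removal, ascertain vital status by the chart review and phone calls already planned, up to one common OS data cut-off date. Censor confirmed survivors at that date, and patients truly lost to follow-up at the date last known alive.

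Alternatively, truncate the reported OS curve and estimates at 12 months from first DEB-TACE. Not every patient will have 12 months at the analysis: it falls 12 months after the last enrolment, while the clock starts at first DEB-TACE, which may be up to 60 days after screening. Late-treated patients should be censored administratively at the cut-off, which is unrelated to removal.

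The first option costs some further chart review or calls for patients removed early. The second costs only wording but gives up the later curve. Neither changes treatment, sample size or the primary analysis.
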